### 7.3 Exclusion Criteria

Subjects who meet any of the following exclusion criteria will not qualify for study participation:

1. Anemia due to a cause other than CKD or presence of active bleeding or recent blood loss.
2. Sickle cell disease, myelodysplastic syndromes, bone marrow fibrosis, hematologic malignancy, myeloma, hemolytic anemia, thalassemia, or pure red cell aplasia.
3. Red blood cell (RBC) transfusion within 4 weeks prior to or during screening.
4. Anticipated to recover adequate kidney function to no longer require hemodialysis during study participation.
5. On peritoneal dialysis or expected to change dialysis modality during study participation.
6. Hypo-responsiveness to ESA defined as any of the following ESA treatments within 8 weeks prior to screening: (i) intravenous epoetin dose  $\geq 3,000$  units/dose 3 times a week (9,000 units/week), (ii) intravenous darbepoetin alfa dose  $\geq 60$   $\mu\text{g}$  once a week, or (iii) epoetin beta pegol  $\geq 200$   $\mu\text{g}$  once a month or  $\geq 100$   $\mu\text{g}$  once every 2 weeks.
7. Aspartate aminotransferase (AST)/serum glutamic oxaloacetic transaminase (SGOT), alanine aminotransferase (ALT)/serum glutamic pyruvic transaminase (SGPT), or total bilirubin  $>2.0$  x upper limit of normal during screening. A history of Gilbert's syndrome is not an exclusion criterion.
8. Uncontrolled hypertension (defined as confirmed pre-dialysis systolic blood pressure [BP]  $>190$  mmHg or diastolic BP  $>110$  mmHg at rest) during screening.
9. Body mass index (BMI)  $>42.0$  kg/m^2.
10. Severe heart failure during screening (New York Heart Association Class III or IV).
11. History of untreated proliferative diabetic retinopathy, diabetic macular edema, age-related macular degeneration, central retinal vein occlusion, active retinal hemorrhage, or ongoing ocular treatment with laser photocoagulation or anti-VEGF therapies.
12. Acute coronary syndrome (hospitalization for unstable angina or myocardial infarction), surgical or percutaneous intervention for coronary, cerebrovascular, or peripheral artery disease (aortic or lower extremity), surgical or percutaneous valvular replacement or repair, sustained ventricular tachycardia, hospitalization for heart failure, or stroke within 12 weeks prior to or during screening.

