### **7.6.2 Conditions and Documentation of Individual Subject Study Drug Discontinuation**

Subjects may discontinue study medication for any of the following conditions:

- Completion of the protocol-defined dosing period (see Appendices
- [Appendix A](#) and [Appendix B](#))
- Worsening of anemia requiring ESA rescue or blood transfusion

- Unacceptable toxicity or drug intolerability
- Investigator discretion
- Subject withdrawal of consent
- Subject becomes pregnant
- Subject receives kidney transplant
- Other reasons

The investigator must document the primary reason for discontinuation in the appropriate case report form (CRF).

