### 9.3.2 Laboratory Evaluations

Samples for laboratory assays will be sent to a central laboratory for analysis. Detailed instructions for the collection, processing, and shipment of laboratory samples will be provided by the sponsor and the central laboratory. The investigator is responsible for reviewing laboratory results for clinical significance.

The following laboratory evaluations will be conducted during the study:

- Serum pregnancy tests: Female subjects who are of childbearing potential (ie, are not surgically sterile or postmenopausal) will participate in serum pregnancy tests (to be analyzed by the central lab). The screening pregnancy test results must be available and must be negative for a subject to initiate study drug.
- Note: Additional serum or local urine (if possible) pregnancy tests may be conducted, as determined by the investigator or required by local regulations, to establish the absence of pregnancy during the study. Coagulation tests: Blood sample will be collected to assess the prothrombin time (PT), partial thromboplastin time (PTT), and international normalized ratio (INR).

- Folate and vitamin B12: Blood sample will be collected to assess folate and Vitamin B12 levels.
- CBC: Blood sample will be collected to assess CBC, including Hb, hematocrit, RBC count, mean corpuscular volume, mean corpuscular Hb, mean corpuscular Hb concentration, red cell distribution width, white blood cell count with differential (neutrophils, bands, lymphocytes, monocytes, eosinophils, and basophils), platelets, and automated reticulocyte count (both absolute and percent).

Blood samples for CBC/Hb assessment will be collected with the patient in the supine position and prior to hemodialysis (per the Japanese Society for Dialysis Therapy [JSDT] guidelines). As noted in Appendices

[Appendix A](#) and [Appendix B](#), the following visits will be scheduled for the first hemodialysis of the week:

- For patients not prescribed ESAs: Screening visit 1, screening visit 2, baseline visit/Day 1, Week 6, Week 16
- For patients prescribed ESAs: Screening visit 2, screening visit 3, baseline visit/Day 1, Week 6, Week 16

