As visit scheduling permits, effort should be made to try to schedule other visits for the first hemodialysis of the week, acknowledging that this may not be feasible due to subject or site scheduling constraints. The CRF will describe how blood samples for central Hb analysis are drawn (ie, supine, prior to hemodialysis, on the day of the first hemodialysis session of the week).

- Chemistry: Including sodium, potassium, bicarbonate, chloride, calcium, phosphorus, glucose, creatinine, blood urea nitrogen, creatine phosphokinase, uric acid, albumin, total protein, total bilirubin, alkaline phosphatase, ALT (SGPT), AST (SGOT), lactate dehydrogenase (LDH), and total cholesterol. Glucose will be measured using plasma samples and the other chemistry parameters will be measured using serum samples.
- Iron indices: Blood samples will be collected to assess serum iron, TIBC, TSAT, and ferritin.
- Hepcidin: Blood samples will be collected to assess hepcidin.
- C-reactive protein: Blood sample will be collected to assess C-reactive protein.
- VEGF: Blood sample will be collected to assess VEGF levels.
- PK analysis: Week 4 pre-dose sample will be analyzed for vadadustat and its metabolites. Study drug dose on this day should be held until after the pre-dose PK sample has been obtained. After the labs are drawn, the subject should take their scheduled dose of study drug.

Blood samples will be collected in tubes with K2EDTA anticoagulant, plasma prepared, and frozen within 1 hour of blood collection. Analysis of samples for vadadustat and metabolite concentration determinations will be performed by a sponsor-designated contract research organization (CRO) using a validated Liquid Chromatography-Mass Spectrometry and Liquid Chromatography-Tandem Mass Spectrometry (LC-MS/MS) method. Detailed instructions for collection, processing, storage, and shipment of the samples for PK and metabolite analyses will be provided by the sponsor or a designated laboratory.

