- No other reason was identified that explains the increased ALT/AST with or without an increased bilirubin (eg, viral hepatitis, acute liver disease).

If new elevations in ALT or AST > 3 times ULN, with or without an elevation of total serum bilirubin > 2 times ULN are identified, the following steps are to be taken:

- Temporary discontinuation of study medication.
- Repeat testing of ALT, AST, ALP and total bilirubin, to be completed within 48 to 72 hours to confirm the abnormalities and to determine trend.
- Study medication should not be resumed until monitoring indicates abnormalities have resolved, are stable, or are not rapidly increasing.

**Worsening of Anemia** – In this study, it is possible that some subjects may experience a worsening of anemia. Worsening of anemia should not be considered an AE unless the worsening of anemia is associated with a cause other than the subject's CKD.

**Kidney Transplantation** – During this study, some subjects may receive a kidney transplant. Kidney transplantation will not be recorded as an AE.

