### 10.3.3 Reporting SAEs

Any SAE, regardless of causal relationship, must be reported to the sponsor's medical monitor/medical director or CRO designee **within 24 hours** after the investigator becomes aware of the SAE. Compliance with this time requirement is essential so that the sponsor may comply with its regulatory obligations.

The initial SAE report should be completed as fully as possible but should contain, at a minimum:

- Subject number/ID, sex, and age/date of birth
- The date of report
- Name of the reporter
- Description of the event, including event term(s), seriousness criteria, and a clinical summary of the event
- Causality assessment

Information about all SAEs (either initial or follow-up information) should be collected and recorded in English on the SAE Report Form. The investigator must assess the relationship to each specific component of the study treatment. If the event meets serious criteria, SAE Report Form should be sent to the CRO via email or fax, or the investigator should call the CRO SAE

hotline within 24 hours of being made aware of the SAE (reference the site manual for contact information).

The investigator must report follow-up information relating to an SAE to the sponsor's medical monitor/medical director or CRO designee within 24 hours of awareness by submitting a new SAE Report Form. The subject should be observed and monitored carefully until the condition resolves or stabilizes.

All deaths are to be thoroughly investigated and reported. Autopsy reports are to be obtained, if possible, and sent to the CRO via email or fax.

The sponsor and/or its designee are responsible for reporting SAEs to all applicable regulatory agencies and the central ethics committees within the required timeline.

The investigators are responsible for submitting required safety information to their local Institutional Review Board (IRB) or Independent Ethics Committee (IEC) per local regulations. This information includes but is not limited to, any safety alert letter received from the sponsor and any SAEs occurring at their investigative site.

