### 10.3.6 Follow-Up of Unresolved Events

All AEs should be followed until they are resolved or the investigator assesses them as chronic or stable or the subject's participation in the trial ends.

In addition, all SAEs and those non-serious events assessed by the investigator as related to the study medication should continue to be followed even after the subject's participation in the trial is over. Such events should be followed until they resolve or until the investigator assesses them as "chronic" or "stable." Resolution of such events is to be documented on the appropriate CRF.

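### The liver-hold restart sentence permits, without requiring, re-dosing while ALT or AST is above 3×ULN and still slowly rising, even with bilirubin above 2×ULN

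*Protocol*

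**What the plan says.** Protocol Section 10.1.1, under the paragraph on ALT, AST and total bilirubin, sets one pathway for a new ALT or AST above 3×ULN, whether or not total bilirubin exceeds 2×ULN. Study drug is stopped temporarily. ALT, AST, ALP and total bilirubin are repeated, "to be completed within 48 to 72 hours to confirm the abnormalities and to determine trend". Restart is governed by one sentence: "Study medication should not be resumed until monitoring indicates abnormalities have resolved, are stable, or are not rapidly increasing". It contains no numeric level, does not define how fast is rapid, and has no separate branch for a combined transaminase and bilirubin elevation.

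Unexplained cases are also reported as an SAE to the medical monitor or CRO designee within 24 hours. Section 10.3.3 adds "The subject should be observed and monitored carefully until the condition resolves or stabilizes", and Section 10.3.6 adds "All AEs should be followed until they are resolved or the investigator assesses them as chronic or stable". Section 7.6.2 lists reasons for which a subject may stop study drug, among them "Unacceptable toxicity or drug intolerability" and investigator discretion.

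**The concern.** A hold rule protects a subject only as far as its restart condition does. Here the weakest of three alternatives is enough, and it is met by values that are above the level that caused the hold and still going up. The same wording covers the subject who has both a transaminase above 3×ULN and bilirubin above 2×ULN.

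What is at stake is patient safety. A subject could be re-exposed to a possible cause of liver injury before the enzymes have levelled off, on the strength of a trend read from two measurements two to three days apart. With about 35 sites for 48 subjects and no definition of a rapid rise, sites may also decide differently in the same situation. None of this would be a protocol deviation.

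**Working it through.** **1. The restart sentence as a condition.** The bar on restart is lifted when: resolved OR stable OR not rapidly increasing. The values below are illustrative.

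| Repeat result | Resolved | Stable | Not rapidly rising | Bar lifted as written | Bar lifted after the fix |
|---|---|---|---|---|---|
| ALT 4.0 then 4.2×ULN, bilirubin normal | no | no | yes | yes | no |
| Same ALT, bilirubin above 2×ULN and slowly rising | no | no | yes | yes | no |
| Same ALT, bilirubin above 2×ULN and rising fast | no | no | no | no | no |
| ALT rising fast | no | no | no | no | no |
| ALT flat at 4.0×ULN, bilirubin normal | no | yes | yes | yes | yes |
| ALT flat at 4.0×ULN, bilirubin flat, above 2×ULN and above own baseline | no | yes | yes | yes | no |

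In the first row ALT rises by 0.2/4.0 = 5% and ends at 4.2/3 = 1.4 times the hold trigger. Calling that rise not rapid is a reading, since the protocol gives no definition, but it is a natural one. The third row assumes that the abnormalities in the restart sentence include bilirubin. That is reasonable, because bilirubin is among the tests repeated in the preceding step.

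**2. Does other text close the gap?**

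- Protocol 7.6.2 is permissive and has no ALT, AST or bilirubin threshold.
- The 24-hour reporting in 10.1.1 informs the medical monitor but gives no role in approving a restart.
- Protocol 10.3.3 and 10.3.6 govern observation and follow-up, not dosing.
- Protocol 8.2.3 unblinds safety personnel for expedited reporting and sets no restart limit.
- SAP 4.8.4.1 only tabulates liver abnormalities.

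None of these sets a restart limit. The hold is also tied to new elevations, so a value that simply stays above 3×ULN after restart does not clearly trigger it again.

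**3. Time to the next scheduled chemistry.** Inputs: Weeks 2, 4 and 6 fall on Days 15, 29 and 43 (Protocol Appendices A and B). The windows are ±1 day for Week 2 and ±3 days for Weeks 4 and 6 (Section 9.1). The repeat is at 2–3 days, counted from the visit date. Formula: gap = next visit day − this visit day − 2 or 3.

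- Nominal: 29 − 15 = 14 and 43 − 29 = 14, so 14 − 3 = 11 to 14 − 2 = 12 days.
- Widest, Week 2 to Week 4: 32 − 14 = 18, so 15–16 days.
- Widest, Week 4 to Week 6: 46 − 26 = 20, so 17–18 days.

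"Samples for laboratory assays will be sent to a central laboratory for analysis", and no turnaround is stated. If the first result takes an assumed 1–3 days, the repeat comes later and the gap shortens. It is then 14 − 6 = 8 to 14 − 3 = 11 days on nominal days, and 18 − 6 = 12 to 20 − 3 = 17 days with the widest windows. All these figures assume no unscheduled test.

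**4. Exposure cost of a tighter rule.** The fixed-dose period is 42 days.

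- One repeat: 2/42 = 4.8% to 3/42 = 7.1%.
- Two repeats: 4/42 = 9.5% to 6/42 = 14.3%.
- Hold to the next nominal visit: 14/42 = 33.3%.

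**The case against.** The strongest reply is that the sentence is a floor. It states what must be true before a restart and leaves the decision to the investigator, who reviews every laboratory result, can stop the drug for toxicity, and must report unexplained cases within 24 hours and send follow-up. No event rate is given, so the text shows a permissive wording and not an expected harm. All of that stands, and it limits the weight of the point. It does not remove it, because none of those safeguards makes the re-dosing in question non-compliant.

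A reader might infer more than the documents support in four ways.

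- *That the protocol directs sites to restart, or disregards bilirubin.* It does neither. The wording is a necessary condition only, and a fast-rising bilirubin keeps the hold in place.
- *That the rule contradicts exclusion criterion 7, which bars entry above 2.0×ULN.* Screening limits select a population and on-study rules manage events, so different thresholds are not an inconsistency.
- *That restart should always wait for ALT and AST at or below 3×ULN.* That would also close the stable route and could keep a subject with an explained, plateaued elevation off drug indefinitely.
- *That a second elevation should force permanent discontinuation.* Nothing in the defect calls for this. A subject stopped before Week 6 has the end-of-treatment assessments early (Protocol 7.6.3), and SAP 4.7.1.3 does not carry that Hb forward. An earlier on-treatment value would then stand in for Week 6, in arms of 12.

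**Conclusion.** The point holds on the text. Section 10.1.1 allows re-dosing with ALT or AST above 3×ULN and slowly rising, and with bilirubin above 2×ULN provided bilirubin is not rising fast. It does not require it, and no other provision sets a restart limit.

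The number of subjects affected cannot be estimated from the documents. The interval with no scheduled chemistry after the repeat is 11–12 days nominally and reaches 15–18 days within the permitted windows. It assumes restart at the repeat, results available on the visit date, and no unscheduled test. The follow-up duties make an unscheduled test likely in unexplained cases but fix no date for it. This is a cheap improvement to patient safety, not a flaw that undermines the trial.

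**What to change.** In Section 10.1.1, delete the last alternative, so that study drug is not resumed until repeat testing shows ALT and AST have resolved or are stable, with stable meaning not rising. Add that, when ALT or AST above 3×ULN occurred together with total bilirubin above 2×ULN, drug is not resumed until bilirubin is at or below 2×ULN or back to the subject's own baseline.

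The baseline alternative is needed because Gilbert's syndrome is allowed at entry: criterion 7 reads "upper limit of normal during screening. A history of Gilbert's syndrome is not an exclusion criterion". The value is already collected, since the Day 1 chemistry panel includes "total bilirubin, alkaline phosphatase, ALT (SGPT), AST (SGOT". Keeping the stable route leaves a way back for a subject with an isolated, explained elevation that has plateaued.

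The cost is a protocol amendment to one rule, with the IRB/IEC approval that Section 15.2 requires. A few subjects would have a longer hold, one more repeat chemistry and some lost exposure before Week 6. With one further repeat the hold is 4–6 days instead of 2–3. A temporarily held subject who attends Week 6 still contributes the actual Week 6 Hb under SAP 4.7.1.3.

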- Adverse event review: Beginning with the first dose of study medication and through the follow-up visit, the investigator and study personnel will review each subject's laboratory and clinical evaluation findings and query the subject directly regarding AEs. Additional information is provided in [Section 10](#) and follow-up of unresolved AEs, serious adverse events (SAEs), and non-serious events is described in [Section 10.3.6](#).
- Rescue therapy (ESA rescue and RBC transfusion) review: Beginning with the first post-baseline visit (after Day 1) and through the follow-up visit, the investigator and study personnel will review whether a subject received rescue therapy (ESA rescue or RBC transfusion).
- Concomitant medication review: All medications taken within 30 days prior to the start of study medication and through the final study visit should be recorded on the appropriate CRF. In addition, the ESA and iron treatment regimen prior to randomization and date of last dose will be recorded.

At each study visit, subjects will be asked whether they have started or discontinued any medication since their previous study visit. This includes single use or as needed medication use. All medications and treatments, including vitamin supplements, over-the-counter medications, and oral herbal preparations must be recorded in the CRFs.

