
**Procedures** – Diagnostic and therapeutic non-invasive and invasive procedures, such as surgery, should not be reported as AEs. However, the medical condition for which the procedure was performed should be reported if it meets the definition of an AE. For example, an acute appendicitis that begins during the AE reporting period should be reported as the AE and the resulting appendectomy noted under “Comments.”

Pre-planned therapeutic procedures not associated with a new medical condition or worsening pre-existing condition should not be reported as AEs.

**Preexisting Conditions** – In this study, a pre-existing condition (ie, a disorder present before the AE reporting period started and noted on the pre-treatment medical history/physical examination form) should not be reported as an AE unless the condition worsens or episodes increase in frequency during the AE reporting period.

**Abnormal Test Findings** – All laboratory test results will be reviewed by the investigator. The investigator will utilize his/her judgment in determining if out of range laboratory values are clinically significant and should denote this using the abbreviation “CS” on the laboratory report for source documentation. Laboratory tests that are labeled as clinically significant should be reported as AEs, either separately or as part of a description of a symptomatic AE. If there are significant changes in a laboratory report from a previous visit that are determined to be clinically significant, these should also be reported as AEs. Any abnormal laboratory value which requires treatment or further diagnostic testing and/or results in discontinuation from study should be reported as AEs. An expected laboratory abnormality from a condition that is part of the medical history is not considered clinically significant for the purposes of the study unless it represents a worsening of the condition.

**Abnormalities in ALT, AST and Total Bilirubin** – Abnormalities in ALT, AST and total bilirubin should be reported to the sponsor’s medical monitor/medical director or CRO designee within 24 hours of awareness as an SAE with ‘other medically important event’ criterion selected, if the following conditions are met:

- New elevation in ALT or AST >3 times the upper limit of normal (ULN), with or without an elevation of total serum bilirubin >2 times ULN, AND

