### 10.1.2 Serious Adverse Events (SAEs)

Each AE must be classified by the investigator as SERIOUS or NONSERIOUS. An AE that meets 1 or more of the following criteria/outcomes is classified as serious:

- Death
- Life-threatening (see paragraph below on Life-threatening)
- In-patient hospitalization or prolongation of existing hospitalization (see paragraph below on Hospitalization)
- Persistent or significant disability/incapacity (see paragraph below on Disability)
- Congenital anomaly/birth defect
- Is considered a medically important event not meeting the above criteria, but which may jeopardize a subject, or may require medical or surgical intervention to prevent one of the criteria listed in this definition.

Serious also includes any other event that the investigator or sponsor judges to be serious. If there is any doubt whether the information constitutes an AE or SAE, the information is to be treated as an SAE.

**Life-threatening** – Any event in which the subject was at risk of death at the time of the event; 'life-threatening' does not refer to an event which hypothetically might have caused death if it were more severe.

**Hospitalization** – Hospitalization is defined as an overnight admission with observation of a minimum of 24 hours. A hospitalization planned before the start of the study for a pre-existing condition that has not worsened during the AE reporting period does not constitute an SAE.

**Disability** – Defined as a substantial disruption in a person's ability to conduct normal life functions.

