### 10.3.1 Reporting Period

The reporting period for all non-serious AEs and all SAEs not related to protocol procedures begins upon receiving the first dose of study medication and ends at the final protocol-required visit.

**SAEs that are assessed by the investigator to be related to protocol procedures (eg, ESA washout) must be reported after signing of the informed consent form.**

In addition, SAEs that occur after the protocol-defined AE reporting period that are considered to be related to the study medication should be recorded and reported to the sponsor's medical monitor or CRO designee.

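### The exemption of worsening CKD anemia from AE reporting makes no exception for serious cases and conflicts with the laboratory-abnormality rule, so serious events may be reported inconsistently or not at all

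*Protocol*

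**What the plan says.** Four parts of the protocol bear on this.

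- **Section 10.1.1, the anemia exemption:** "Worsening of anemia should not be considered an AE unless the worsening of anemia is associated with a cause other than the". The disease named at the end of that sentence is the subject's CKD. The paragraph, headed Worsening of Anemia, does not mention hospitalization, life-threatening events or any other seriousness criterion.
- **Section 10.1.1, Abnormal Test Findings:** "Any abnormal laboratory value which requires treatment or further diagnostic testing and/or results in discontinuation from study should be reported as AEs". There is no exception for Hb.
- **Section 10.1.2:** "An AE that meets 1 or more of the following criteria/outcomes is classified as serious". Two general sentences come after the list. The first reads "Serious also includes any other event that the investigator or sponsor judges to be serious". The second deals with uncertainty: "If there is any doubt whether the information constitutes an AE or SAE, the information is to be treated as an SAE".
- **Section 10.3.1:** SAEs that the investigator judges "related to protocol procedures (eg, ESA washout) must be reported after signing of the informed consent form".

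Section 10.3.3 attaches the 24-hour report to SAEs. Section 8.2.6 requires a subject who starts ESA or transfusion rescue to stop study drug and leave the study, and section 7.6.2 lists worsening anemia that needs rescue as a reason for stopping.

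**The concern.** It is reasonable not to collect every routine Hb decline as an AE in an anemia trial. The difficulty is that the exemption is written without an upper limit. The protocol withholds ESA from every subject and gives placebo to one arm for six weeks, so worse anemia is a foreseeable harm of the design. If a site applies the exemption literally, an admission for CKD anemia does not reach the seriousness criteria and the sponsor is not alerted within 24 hours. If another site applies the laboratory rule, the same event is an SAE leading to withdrawal. The safety tables would then partly reflect which paragraph a site followed. SAP section 4.8.6 marks a data monitoring committee as not applicable, so expedited SAE reports carry much of the safety signal while the trial is running.

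**Working it through.** No formula applies, and the plan gives no figure on this point to reproduce. The check is to trace an event through the rules.

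**Case A: a placebo subject at Week 4 whose Hb falls, who is admitted for more than 24 hours and transfused, with CKD as the only cause.**

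1. Transfusion is rescue, so the subject stops study drug and is discontinued (sections 8.2.6 and 7.6.2).
2. Under Worsening of Anemia (10.1.1) this is not an AE.
3. Under Abnormal Test Findings (10.1.1) it is an AE on two grounds: the Hb value needed treatment and it led to discontinuation. That paragraph's own allowance for expected abnormalities stops applying once the underlying condition has worsened. The opening list of 10.1.1 also counts worsening of an existing illness as an AE.
4. If step 3 governs, the admission makes it an SAE (10.1.2) with a 24-hour report (10.3.3). If step 2 governs, the list in 10.1.2 is not reached. What remains is the clause on any other event judged serious, which depends on individual judgment. The doubt rule decides between AE and SAE; it does not decide whether something is an AE at all.
5. In the SAP, the step 3 route puts the event in the tables of treatment-emergent SAEs and of TEAEs leading to withdrawal (4.8.2). The step 2 route puts it in neither. It then appears only in the rescue and ESA summaries (4.7.3) and in withdrawals by reason (4.3.1).

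**Case B: a subject in ESA washout whose Hb falls and who is admitted.**

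1. If the cause is recorded as CKD, the exemption applies. If it is recorded as ESA withdrawal, it does not.
2. Three places favor the second reading: 10.3.1 names ESA washout as its example, the list in 10.1.1 includes events secondary to withdrawal of a medication, and 10.3.4 offers a protocol-related procedure as a possible cause.
3. The Worsening of Anemia paragraph does not itself say that ESA withdrawal counts as a cause other than CKD, so the attribution is left to the site.
4. The rescue review does not serve as a second source here, because it runs "Beginning with the first post-baseline visit (after Day 1) and through the follow-up visit". AE review and a CBC are, however, scheduled at every screening visit (sections 9.4 and 9.5, Appendices A and B).

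**Scale.** Each arm has 12 planned subjects. Moving one event into or out of an arm's SAE count changes its rate by 1/12 = 8.3 percentage points. This shows how sensitive the table is; it does not predict how many events will occur.

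**The case against.** The strongest reply is that the anemia paragraph is a deliberate, study-specific exception to general rules and that other provisions catch what it leaves out. Much of this stands.

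- A reader might infer that serious CKD anemia can never be an SAE. The documents do not support that. Section 10.1.2 extends seriousness to any other event that the investigator or sponsor judges serious, and 10.3.3 requires all deaths to be investigated and reported. The first clause is discretionary, so it narrows the gap without making sites consistent.
- A reader might infer that a serious washout event has no place in the data. That is also too strong. Section 10.3.1 points towards reporting, AEs and CBC are reviewed at each screening visit, reasons for ineligibility are logged (9.2.2), and SAP 4.8.2 tabulates procedure-related SAEs in screening. That table is by treatment group, so a subject who was never randomized would have no column. Rewording the exemption does not change this.
- After Day 1 the harm of withholding ESA is not invisible. Rescue is reviewed at each post-baseline visit and compared by arm with Fisher's exact test (SAP 4.7.3). Separate clinical events such as cardiac failure are not exempted. These summaries are not 24-hour safety reports, however.
- Not every rescue exposes the conflict. Rescue for a cause other than CKD is already an AE, and ESA rescue also depends on investigator judgment and clinically significant worsening or symptoms.

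Reading the specific paragraph as overriding the general one explains why routine Hb decline is exempt. It does not explain the silence on serious cases.

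**Conclusion.** The point holds as a conflict of wording that should be fixed. The exemption has no exception for seriousness and contradicts the Abnormal Test Findings paragraph of its own section. Serious anemia attributed to CKD may therefore go unreported or be reported inconsistently, mainly after Day 1, where CKD is the natural attribution. For washout the case is weaker, because a reading that gives effect to both 10.1.1 and 10.3.1 is available, although the protocol does not state it.

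The size cannot be quantified. It would be tempting to use the share of placebo subjects expected below the 9.0 g/dL rescue level, but an Hb below that level is not in itself worsening, rescue or a serious event, so such a share says nothing about an SAE rate. The conclusion rests on the text alone and assumes only that some sites will apply the exemption as written.

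**What to change.** 1. In section 10.1.1, limit the Worsening of Anemia exemption to worsening that meets no seriousness criterion in 10.1.2.
2. State there that worsening anemia meeting any such criterion is reported as an SAE whatever its attribution, and from informed consent when related to ESA washout, as 10.3.1 already provides.
3. Add a cross-reference in Abnormal Test Findings saying how it applies to Hb, so that the two paragraphs give one answer for a low Hb that leads to rescue.
4. In SAP section 4.8.2, confirm that these serious events count in the SAE tables and in the tables of AEs leading to withdrawal, alongside the rescue summaries in 4.7.3.

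The cost is a few sentences in the protocol and SAP, a memo to sites and a small number of additional SAE reports. Only reporting changes; treatment and rescue rules are untouched.
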